13.11. Recording Adverse Events

Adverse events spontaneously reported by the participant and/or in response to an open question from the study personnel or revealed by observation will be recorded during the study at the investigational site. Clinically significant changes in laboratory values, blood pressure, and pulse need not be reported as AEs. However, abnormal values that constitute an SAE or lead to discontinuation of administration of study drug must be reported and recorded as an AE. Information about AEs will be collected from the signing of consent until the end of the LTFU. Serious Adverse Event information will be collected from the signing of consent form until the end of the LTFU. The AE term should be reported in standard medical terminology when possible. For each AE, the investigator will evaluate and report the onset (date and time), resolution (date and time), intensity, causality, action taken, serious outcome (if applicable), and whether or not it caused the participant to discontinue the study.

AE intensity will be assessed according to NCI CTCAE v5.0.

It is important to distinguish between serious and severe AEs. Severity is a measure of intensity whereas seriousness is defined by the criteria under Section 13.9.1.2. An AE of severe intensity may not be considered serious.

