13. SAFETY PARAMETERS

13.1. Vital Signs, Height, and Weight

Vital signs will be measured after the participant has been at rest. Measurements will include systolic and diastolic blood pressure, pulse rate per minute, respiratory rate per minute, and temperature. Height will be measured in centimeters as the length of the participant in the supine position. Weight will be recorded in kilograms.

A vital sign result should be reported as an AE if it meets any of the following criteria:

- Accompanied by clinical symptoms
- Results in a medical intervention or a change in concomitant therapy
- Clinically significant in the investigator's judgement

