13.4. Laboratory Assessments

Laboratory assessments for safety will be performed by the site's local laboratory, and all certification/qualification documentation will be on file in the TMF. A laboratory test result should be assessed as clinically significant or not clinically significant, and should be reported as an AE if it meets any of the following criteria:

- Accompanied by clinical symptoms
- Results in a medical intervention or a change in concomitant therapy
- Clinically significant in the investigator's judgement

If a clinically significant laboratory abnormality is a sign of a disease or syndrome (e.g., hemoglobin below the lower limit of normal associated with anemia), only the diagnosis should be recorded. If the abnormality is not a sign of a disease or syndrome, the abnormality itself should be recorded (e.g., low calcium).

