13.9. Adverse and Serious Adverse Events

13.9.1. Definition of Adverse Events

13.9.1.1. Adverse Event (AE)

According to the International Conference of Harmonization (ICH) guideline for Good Clinical Practice, an AE is any untoward medical occurrence in a patient administered pharmaceutical product and which does not necessarily have a causal relationship with this treatment.

An AE can therefore be any of the following:

- Unfavorable and unintended sign (including an abnormal laboratory finding), symptom, or disease temporally associated with the use of a medicinal (investigational) product, whether or not considered related to the medicinal (investigational) product.
- Any new disease or exacerbation of an existing disease (a worsening in the character, frequency, or severity of a known condition)
- Recurrence of an intermittent medical condition (e.g., headache) no present at baseline
- Any deterioration or abnormality in a laboratory value or other clinical test (e.g., ECG, X-ray) that is associated with symptoms or leads to a change in the study treatment or concomitant treatment or discontinuation from the study drug
- Adverse events that are related to a protocol-mandated intervention, including those that occur prior to assignment of study treatment.

All AEs will be captured following the signing of the informed consent form.

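### Section 13.11 waives AE reporting for clinically significant laboratory, blood pressure and pulse changes that Sections 13.1 and 13.4 say should be reported, so some non-serious events may drop out of the Stage 1 primary endpoint and the stopping criterion 3 count

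*Combined protocol and SAP*

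**What the plan says.** Three sections give recording rules for the same kind of finding.

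- **Section 13.11 (Recording Adverse Events):** "Clinically significant changes in laboratory values, blood pressure, and pulse need not be reported as AEs". The next sentence restores mandatory recording only for abnormal values that are SAEs or that lead to stopping study drug administration. The section also notes that a severe AE need not be a serious one.
- **Section 13.4 (Laboratory Assessments):** a laboratory result "should be reported as an AE if it meets any of the following criteria": accompanying symptoms, a resulting intervention or change in concomitant therapy, or being "Clinically significant in the investigator's judgement". Where the abnormality is a sign of a disease or syndrome, "only the diagnosis should be recorded".
- **Section 13.1 (Vital Signs, Height, and Weight):** "A vital sign result should be reported as an AE if it meets any of the following criteria", with the same three criteria. Blood pressure and pulse are among the vital signs listed.

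The AE definition in Section 13.9.1.1 counts an abnormal laboratory finding among unfavorable signs. A separate bullet covers a laboratory deterioration "that is associated with symptoms or leads to a change in the study treatment or concomitant treatment". The section closes with "All AEs will be captured following the signing of the informed consent form".

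**The concern.** Clinical significance on its own triggers reporting in Sections 13.1 and 13.4, and it is the property that Section 13.11 releases from reporting. An investigator can follow either text and be compliant, and with up to three sites, practice may differ.

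Three uses of the AE record depend on the answer:

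- the Stage 1 primary endpoint, which is the incidence, severity, seriousness and relatedness of TEAEs (Section 1);
- stopping criterion 3 in Section 9.4, which counts related AEs of Grade 3 or higher within a participant and does not require seriousness;
- the option in Section 8.1.1.1 to add a participant to a dose level after a related AE of Grade 3 or higher in the first 4 weeks.

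Stage 1 has 12 participants spread over four dose levels, so a single omitted event is a visible part of the safety picture.

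**Working it through.** The plan states no figure on this point. The check compares the rules and then counts events.

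**1. Do the rules conflict?**

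| Finding (non-serious) | Sections 13.1 / 13.4 | Section 13.11 |
|---|---|---|
| Laboratory value judged clinically significant | Should be reported | Need not be reported |
| Blood pressure or pulse judged clinically significant | Should be reported | Need not be reported |

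**2. Do the exceptions in Section 13.11 close the gap?** There are two. Stopping study drug administration can apply only while the product is being given, and Section 8.1 places the last infusion on Day 2. After that only the SAE exception remains. Because Section 13.11 itself separates severity from seriousness, a non-serious Grade 3 value falls outside it.

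**3. Does another section set precedence?** No. Section 13.9.1.1 leans towards Sections 13.1 and 13.4, but it does not name blood pressure or pulse, its specific laboratory bullet turns on symptoms or a treatment change, and it does not claim to override Section 13.11. The DSMC Charter was not among the documents reviewed.

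**4. What happens to the counts?** For one participant, with all events related, Grade 3 or higher and non-serious, let

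- *s* = laboratory abnormalities separately recordable under Section 13.4, after the diagnosis-only rule;
- *c* = other AEs recorded in any case, including any qualifying symptom recorded in its own right.

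Count under Section 13.4 = *c* + *s*. Count under Section 13.11 = anything from *c* to *c* + *s*, because the waiver is permissive. Criterion 3 needs a count of at least 2.

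| Case | *c* | *s* | Under 13.4 | Under 13.11 | Criterion 3 |
|---|---|---|---|---|---|
| A: two separate laboratory abnormalities | 0 | 2 | 0 + 2 = 2 | 0 to 2 | Met under 13.4; may be unmet under 13.11 |
| B: one clinical AE and one separate laboratory abnormality | 1 | 1 | 1 + 1 = 2 | 1 to 2 | Met under 13.4; may be unmet under 13.11 |
| C: two values that are signs of one diagnosis, or only one reportable value | 0 | 1 | 0 + 1 = 1 | 0 to 1 | Not met under either |
| D: no reportable value | 0 | 0 | 0 | 0 | Not met under either |

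The sections can disagree on criterion 3 only when *c* is below 2 and *c* + *s* is at least 2. Blood pressure and pulse events follow the same arithmetic through Section 13.1.

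For the additional-participant option the threshold is 1. With *c* = 0 and *s* = 1 before 4 weeks, the count is 1 under Section 13.4 and 0 to 1 under Section 13.11.

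**5. Which stopping criteria are exposed?** One of four. Criteria 1 (related death), 2 (hemorrhage or herniation) and 4 (related SAE) do not depend on the waiver. An event the investigator judges medically significant is an SAE under Section 13.9.1.2 and, if related, meets criterion 4 alone.

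**The case against.** The best case on the other side accepts the wording conflict and disputes its weight.

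*Little is lost in practice.* Criterion 3 leads to a temporary suspension and DSMC review. In Stage 1 the DSMC already reviews safety before each dosing (Section 8.1.1.1) and sees clinical laboratory data (Section 17.1). Laboratory and vital-sign changes are Stage 1 secondary endpoints, Stage 1 analysis is mainly graphical (Section 14.2), and participants can be added at the DSMC's request regardless. All of this is true and keeps the point from being more serious. But these safeguards show raw values. They do not put an event back into a TEAE table or into a count defined on AEs.

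*The exposed set is narrow.* Section 13.11 still records AEs seen or reported, so a symptom accompanying an abnormal value remains recordable. That stands, and *c* above allows for it. The exposure is cleanest for values that qualify on clinical significance alone.

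*The AE definition settles the matter.* It favors Sections 13.1 and 13.4, but a general definition does not cancel an explicit later waiver without saying so.

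*The correction brings problems of its own.* One worry is that keeping the SAE sentence as an addition could lead to a value being recorded beside its diagnosis. That sentence is already in the protocol, and a related SAE meets criterion 4 alone, so a double count could not change whether enrollment is suspended. The other is that Section 13.9.1.3 defines AESIs by laboratory thresholds, for instance platelets below 150,000/μL, which need not meet a Section 13.4 criterion. That mismatch is real, but it exists already and is not created by the correction.

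**Conclusion.** The concern holds and should be fixed. The contradiction is direct and no section resolves it, so confidence in the textual conflict is high. Its effect is conditional. It needs non-serious laboratory, blood pressure or pulse events and a site that uses the waiver. For criterion 3 they must also be related, Grade 3 or higher, and in a combination that reaches 2 only when they are counted. In those cases a count of 2 can fall to 1 or 0 and the criterion goes unmet; for the additional-participant option a count of 1 can fall to 0. How often this would happen cannot be estimated from the documents.

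**What to change.** In Section 13.11, replace only the waiver sentence with: *Laboratory and vital-sign abnormalities are recorded as AEs according to Sections 13.1 and 13.4.* Keep the following sentence on SAEs and discontinuation, and change its opening word from *However* to *In addition*. The diagnosis-only rule in Section 13.4 then applies unchanged. Adding Section 13.9.1.3 to the cross-reference would be a sensible extra, so that the laboratory-defined AESIs are covered too.

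The cost is one replaced sentence and one changed opening in the protocol, a note to sites, and slightly more AE entries.

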13.12. Reporting Adverse Events

All SAEs (related and unrelated) occurring from the signing of consent form until the completion of the LTFU must be reported to the Sponsor or designee within 24 hours of the investigator's knowledge of the event. Any SAEs considered possibly or probably related to the investigational product and discovered by the Investigator at any time after the study should be reported. All SAEs must be reported to [name] within 24 hours of the first awareness of the event.

The Investigator must complete, sign and date the SAE pages, verify the accuracy of the information recorded on the SAE pages with the corresponding source documents, and send a copy by fax to Dr.[name] at UMass Chan Medical School.

Additional follow-up information, if required or available, should all be faxed to UMass Chan Medical School within one business day of receipt and this should be completed on a follow-up SAE form and placed with the original SAE information and kept with the appropriate section of the CRF and/or study file. All participants with a SAE must be followed up and the outcomes reported until the event has returned to baseline status or resolved.

SAE reporting will originate in the electronic data capture (EDC) system and an email will be sent to the designated responsible parties in Safety. The paper SAE form is in place as a back-up in the event that EDC is not accessible to the reported of the SAE:

- [contact]
- Provide copy of all relevant source documents, including medical history, hospital records and discharge summaries, and concomitant medication pages, as appropriate

Confidential Page 81 of 97

Clinical Study Protocol: AXO-GM2-001

Version 8.0, 09 June 2023

UMass Chan Medical School is responsible for notifying the relevant regulatory authorities of certain events.

It is the Principal Investigator's responsibility to notify the IRB or IEC of all SAEs that occur at his or her site. Investigators will also be notified of all unexpected, serious, drug-related events (7-day and 15-day Safety Reports) that occur during the clinical trial. Each site is responsible for notifying its IRB or IEC of 15-day or 7-day safety reports required by local regulations or IRB/IEC requirements and shall provide the sponsor or its designee with written confirmation of said IRB/IEC notification.

13.13. Reporting Device Deficiencies

Any deficiency in the AXO-AAV-GM2 administration system defined as an inadequacy with respect to identity, quality, durability, reliability, safety or performance which includes malfunctions, use errors, and inadequate labeling will be recorded in the eCRF and reported immediately to the sponsor and the equipment quarantined.

Device deficiencies that did not lead to an AE but could have led to a medial occurrence should also be reported (e.g.):

- a. if suitable action had not been taken
- b. if intervention had not been made, or
- c. if circumstances had been less fortunate

The sponsor will review all device deficiencies and determine and document in writing whether they could have led to a serious adverse device effect (SADE) and report in accordance with regulations to all relevant parties.

Confidential Page 82 of 97

AXO-AAV-GM2

UMass Chan Medical School Clinical Study Protocol: AXO-GM2-001

Version 8.0, 09 June 2023

14. STATISTICS

The statistical analysis methods for Stage 1 and Stage 2 will reflect the design elements and objectives of each Stage, with descriptive methods and data listings the primary methods used for the Stage 1 data, and with a focus on descriptive methods used for the Stage 2 data. Potential comparison of outcomes to external control data may be performed and will be described in the statistical analysis plan.

14.1. Sample Size

- Stage 1: The objectives of Stage 1 is to evaluate safety and identify the dose to be used in Stage 2. A sample size of N=1 or 2 participants per dose, is expected to allow for differentiation of outcomes sufficient to select the 'better' dose. This determination is based on an understanding of the target indication and expected characteristics of the study treatment, and thus is not based on specific hypothesis-testing assumptions.
- Stage 2: The Primary Efficacy Endpoints for Stage 2 will be the BSID-III Gross Motor domain change from baseline to Week 48 (Month 12) and CSF HexA activity change from baseline to Week 48 (Month 12). The sample size is not based upon hypothesis testing assumptions but rather the desire to assess neurodevelopment of participants at ages when they would be expected to be declining based on natural history data.

14.2. General Methods

Stage 1 includes 12 participants at differing doses of AXO-AAV-GM2 which precludes tabulation of outcomes in a mathematically reasonable manner. Thus, the analysis of Stage 1 outcomes will focus comparisons of individual participant data using graphical displays (e.g., line-scatterplots of each participant's outcomes over time) to allow for visual inspection of any trends between participants. Limited tabulations may be created to present overall Stage 1 data (e.g., as for adverse event incidence), as the data warrant. The methods provided below are generally intended to describe the analysis of Stage 2 outcomes but may also apply to Stage 1 in some instances (e.g., adverse event coding).

Stage 2 will include a comprehensive assessment of both efficacy and safety outcomes, with tables, listings, and figures generated. Data will be tabulated and presented using both descriptive and inferential statistics (where applicable) where specified. Select continuous endpoints will be assessed a mixed model for repeated measures (MMRM) of changes over time with effects for visit, the baseline value (of the outcome of interest), and a random effect for participant. Graphical displays of least squares mean (LSMean) changes over time will be presented.

The statistical analysis will be undertaken by the Sponsor or a third-party vendor. The statistical analysis and report will conform to the relevant ICH requirements.

SAS version 9.4 or later will be used for the analysis.

There is no formal hypothesis being tested. However, comparison to external data sources (e.g., literature, NH studies) may be performed as the data allow.

Confidential Page 83 of 97

Version 8.0, 09 June 2023

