14.4. Primary Efficacy Endpoints

The Primary Efficacy Endpoints are:

- Clinical Function: BSID-III Gross Motor domain
 - The continuous clinical outcome BSID-III Gross Motor domain will be assessed as a change from baseline to Week 48 (Month 12).
- Surrogate Biologic Marker: CSF HexA activity
 - CSF HexA activity will be assessed as a change from baseline to Week 48 (Month 12), including the baseline (pre-treatment) value as a covariate in the model.

This is an open-label, single-arm study in which outcomes will be compared to a pre-specified external (e.g., NHS) study database or to the literature. There is no alpha-control applied for having co-primary endpoints as no formal hypothesis testing is planned.

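### Does the Stage 2 mixed model in Section 14.2 need a stated residual covariance and degrees-of-freedom method to give a sound Week-48 standard error?

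*Combined protocol and SAP*

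**What the plan says.** Section 14.2 (General Methods) contains the only model stated for Stage 2: "Select continuous endpoints will be assessed a mixed model for repeated measures (MMRM) of changes over time". Which endpoints are meant is not said. The terms that the section then lists for this model are "effects for visit, the baseline value (of the outcome of interest), and a random effect for participant". The planned output is graphical: "Graphical displays of least squares mean (LSMean) changes over time will be presented". On inference the section says: "Data will be tabulated and presented using both descriptive and inferential statistics (where applicable) where specified". SAS 9.4 or later is named as software. No residual covariance, degrees-of-freedom method or convergence fallback appears anywhere, and Table 4 only expands the abbreviation MMRM.

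Section 14.4 (Primary Efficacy Endpoints) sets both primary endpoints at Week 48. For CSF HexA it speaks of "including the baseline (pre-treatment) value as a covariate in the model" without saying which model; for BSID-III Gross Motor it names none. It adds that "outcomes will be compared to a pre-specified external (e.g., NHS) study database or to the literature", and that no formal hypothesis test and no alpha control are planned.

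Section 14 describes the analysis "with a focus on descriptive methods used for the Stage 2 data". The Synopsis (Statistical Methods and General Methods) says the Stage 2 models will be built on Stage 1 data and set out in a statistical analysis plan. No separate plan of that kind is among the documents supplied.

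**The concern.** A random participant intercept with independent, equal-variance residuals implies compound symmetry: one variance for every visit. A Week-48 least squares mean from such a model takes its standard error from the pooled variance over all visits, not from the spread at Week 48. Visits run from Week 4 to Week 48 in a rapidly progressive disease, so equal spread is a strong assumption.

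If MMRM is instead taken to mean an unstructured covariance, the standard error is specific to the visit, but the stated random intercept is then redundant. Two programmers could follow the sentence and report different Week-48 intervals from the same data.

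What would be at stake is the precision shown for the two Week-48 primary endpoints in up to 10 children, and so how any comparison with natural-history data is read.

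**Working it through.** **Inputs from the documents.** Stage 2 enrols up to 10 children (Section 8.1.2); n = 10 is used. BSID-III is measured at Weeks 4, 12, 24 and 48, and post-treatment CSF HexA at Weeks 12, 24 and 48 (Table 15). Neither is done at Week 48 if that visit is by tele-health (Table 15, footnote 23). The documents give no SDs, correlations or standard errors, so there is no figure of the plan to reproduce.

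**Assumptions.** The SD of change is linear in weeks, from 1 at the first post-treatment visit to r at Week 48. Correlation is 0.7 per visit step, the true mean change is 0, and 95% intervals use Satterthwaite degrees of freedom.

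**Formula.** With complete data and the default residual, the standard error at every visit is √(mean of visit variances / n), apart from a small effect of estimating the baseline slope. The correct Week-48 value is √(Week-48 variance / n). Hence

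SE ratio = √(mean visit variance / Week-48 variance).

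**BSID-III, r = 1.5.** The SDs are 1, 1.09, 1.23 and 1.5. The mean variance is 1.487 and the ratio is √(1.487 / 2.25) = 0.81.

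**CSF HexA, r = 1.5.** The SDs are 1, 1.17 and 1.5. The mean variance is 1.537 and the ratio is √(1.537 / 2.25) = 0.83.

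| r | BSID-III SE ratio | Coverage | CSF HexA SE ratio | Coverage |
|---|---|---|---|---|
| 0.6 | 1.42 | 99% | 1.40 | 99% |
| 0.8 | 1.15 | 97% | 1.14 | 97% |
| 1.0 | 1.00 | 95% | 1.00 | 95% |
| 1.2 | 0.90 | 93% | 0.91 | 93% |
| 1.5 | 0.81 | 89% | 0.83 | 90% |
| 2.0 | 0.73 | 85% | 0.75 | 86% |

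Coverage is simulated (40,000 replicates per scenario). A repeat with 20,000 replicates agreed within about one point. A direct REML fit to one simulated data set with SDs 1, 1.5, 2 and 3 gave 0.432 at all four visits, against visit-specific standard errors of 0.230, 0.356, 0.468 and 0.554. The algebra is therefore right for that version of the model.

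**Degrees of freedom.** The t multiplier is 2.05 on 27 df and 2.31 on 8 df, so interval width changes by 2.31 / 2.05 − 1, or about 12%.

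**Does the text impose that version?** Section 14.2 is silent on the residual. Two other fits are open to an analyst:

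- *Random intercept with visit-specific residual variances.* This keeps every stated term. It has 1 + 4 = 5 parameters for four visits and is identifiable. Under the same assumptions the Week-48 SE ratio is 0.97 to 1.00 at r = 1.5 and 0.94 to 0.95 at r = 2 (the ranges are from two separate sets of fits). At r = 0.6 it is 1.24, so some overstatement remains.
- *Unstructured covariance.* Four visits have 4 × 5 / 2 = 10 variances and covariances; adding a random intercept makes 11 parameters (CSF HexA: 6 and 7). The extra parameter is redundant, but the marginal covariance is still identified, and it alone sets the least squares mean and its standard error. The result is a software warning or a boundary estimate, not a wrong Week-48 standard error.

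**Price of prescribing an unstructured covariance.** If variances are in fact equal, its intervals are wider than the pooled model's by 6–8% with complete data at n = 10, 10–11% with 2 of 10 missing Week 48, and 16–21% with 2 of 8 missing. BSID-III fits fail in 0%, up to 0.3%, and 5–6% of data sets respectively.

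**The case for a change.** The strongest case for a change is that Section 14.2 already commits to a random participant effect, so copying it into the analysis plan would carry the ambiguity along. Inferential statistics are allowed, Section 14.4 promises an external comparison, and settling the covariance after seeing Stage 2 data would be open to question. Missing Week-48 values are realistic because of tele-health visits. With 2 of 10 missing completely at random, the pooled-variance model covers 88% at r = 1.5 and 83% at r = 2 for BSID-III. With missing data the covariance also affects the point estimate, which it does not with complete data.

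Much of this stands: the detail is absent, and the pooled-variance algebra is correct. What does not stand is that the sentence is wrong as written. The equal-variance residual has to be supplied by the reader, the random effect can stay, and the use of this model for the primary endpoints is itself inferred. The model behind CSF HexA in Section 14.4 could equally be a Week-48 ANCOVA.

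Nor do the documents show which way spread moves. Section 5 reports that gross motor scores reached the test floor by 28 months in all tested patients, which could compress the spread at Week 48; uneven response to treatment could widen it.

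**Conclusion.** No change is called for. This is detail left to the analysis plan, and analysts would fill it sensibly: they would name the endpoints, allow the variance to differ by visit and choose a small-sample degrees-of-freedom method.

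The worst figures (SE ratio 0.73 or 1.42, coverage 85% or 99%) need three things together: default residuals, use of the model for the Week-48 primary endpoints, and an SD ratio of 2 or 0.6 that nothing in the documents supports or excludes. Between ratios of 0.8 and 1.2, coverage stays within about 2 points of 95%. With complete data the point estimates are untouched, and no test, alpha level or decision rule depends on the interval.

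Prescribing one structure now would bring no clear gain. An unstructured covariance in up to 10 children protects against unequal variances at the cost of intervals 6–21% wider if variances are equal, with some non-convergence. Reasonable statisticians differ on that trade, and the Synopsis intends to decide it with Stage 1 data in hand. The simulated figures rest on normal data, the assumed SD pattern and correlation, and Week-48 values missing completely at random.
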